## **1. Name of research**

Component Analysis of Surgical Smoke and Evaluation of Reduction through the Use of Smoke Evacuator Devices

### **3. Purpose and Significance of the Study**

[Background] It is known that smoke (surgical-related smoke) is generated when energy devices (electrocautery, vascular coagulation devices, etc.) are used during surgery. It is known that smoke contains toxic substances [1, 2], but it is unknown which components and to what extent, and how much of the toxic substances in the smoke can be removed by using surgical smoke evacuation devices that are commercially available for medical use. Several companies sell smoke evacuation devices for medical use, but their use is not widespread. Our operating room does not have a surgical smoke evacuation system, and it is not used during surgery. We hypothesized that the use of surgical smoke evacuation devices removes toxic substances from smoke, and planned a clinical study to verify this hypothesis.

[Purpose] In this study, we will conduct a multicenter study on the types and amounts of toxic substances in surgical smoke by randomly assigning patients to use or not to use surgical smoke evacuation devices to verify our hypothesis and the preliminary results of a small number of cases. The findings of this study will lead to a wider recognition of the harmfulness of surgical smoke and the usefulness of surgical smoke evacuation devices and may lead to the prevention of health hazards for healthcare workers in the operating room in the future.

[In this study, we randomly assigned patients to use or not to use surgical smoke evacuation devices to examine the types and amounts of hazardous substances in surgical smoke to verify the hypothesis and the results of a preliminary study using a small number of cases. The findings of this study will lead to a wider awareness of the

harmfulness of surgical smoke and the usefulness of surgical smoke evacuation devices and may lead to the prevention of health hazards for healthcare workers in the operating room in the future.

[References]

1. Limchantra, I. V., et al. (2019). "Surgical Smoke Exposure in Operating Room Personnel: A Review. "JAMA Surg.
2. Al Sahaf, O. S., et al. (2007). "Chemical composition of smoke produced by high-frequency electrosurgery," *Ir J Med Sci* 176(3): 229-232.

#### **4. Methods and duration of the study**

[Methods]

This is an observational study without invasive intervention.

The study will be conducted with those who have obtained a consent form (page 16) after the explanation of the study is provided in the Explanation Document (pages 13-15). The Consent Withdrawal Document (page 17) will also be distributed to provide an opportunity for withdrawal after consent has been given.

2. Patients who meet the inclusion criteria and have given consent will be assigned to the surgical smoke evacuation device use group (A) or non-use group (B) without the knowledge of the operating physician. At this point, patients will be anonymized with a "subject identification code" that will be set up at the facility to enable the linking of subjects.

##### **3A. Intervention group (surgical smoke evacuation system)**

A surgical smoke evacuation device (Vigilia Smoke Evacuation System, model no. VC120, ConMed) and smoke suction tube (22 mm x 3.0 m smoke evacuation tube, model no. VTWT624, ConMed) were used (ConMed). ConMed) (Figure 1). The smoke suction tube is placed so that the tip of the tube is 5 cm from the planned incision at the time of laparotomy, as it is used in actual clinical practice. The surgical smoke evacuation device is placed about 1 m away from the operating table, as used in actual clinical practice. The smoke evacuation device is switched on at the start of the laparotomy procedure.

Figure 1

3B. Control group (no use of surgical smoke evacuation device)

The same preparation and procedures as in 3A are performed, but the surgical smoke evacuation device is not connected to the smoke suction tube. (This is to reduce the bias of the surgeon to know whether the smoke evacuation device is used or not.

4. A sterile cover is placed over a table (20 cm headward and 20 cm above the upper edge of the planned incision) on which a small smoke collection device is placed approximately above the patient's face (1) Mini-pump, model number: MP-W5P, Shibata Scientific Corporation, [Figure 2]) (2) Particle counter, model number: Model 804, Shibata Kagaku Corporation, [Figure 3]). Collect for 10 minutes from the start of the operation. 5.

5. The collected smoke is analyzed at the Environmental Technology Center co., Ltd outside the university to which the co-researcher belongs, with a subject identification code assigned.

Figure 2

Figure 3

[Period]

Registration Period/Subject Period: From the date of approval to March 31, 2022

Institution: From the date of approval to March 31, 2023

[Anonymization]

Subjects will be anonymized by the "subject identification code" set in the institution as described above to enable linking. The principal investigator or co-investigator at the collaborating institution will use a "subject identification code" that is unrelated to the subject's name and hospital ID and register the subject with that number. The code will be used only for this study. No personally identifiable information will be used when the results of the study are published.

[Analysis method]

The Student's t-test will be used to compare the detected amounts of acetaldehyde, formaldehyde, and emissions by particle size in the two groups (surgical smoke evacuation device-using group vs. non-user group).

[primary endpoint]

Quantitative measurement of acetaldehyde in surgical smoke.

To verify whether the surgical smoke evacuation device reduces the amount of the above toxic substances.

[Secondary endpoint]

Quantitative measurement of formaldehyde in surgical smoke.

Measurement of emissions by particle size in surgical smoke (measurement by 0.3 $\mu$ m, 0.5 $\mu$ m, 1 $\mu$ m, and 2 $\mu$ m is possible).

Also, evaluate the differences in formaldehyde and particle size emissions using surgical smoke evacuation equipment.

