## **5. Selection of research subjects**

[Number of research subjects] Overall expected number of subjects: 40 cases (40 cases at the University of Tokyo)

[Selection criteria]

1. Inclusion criteria

Patients aged 20 years or older undergoing laparotomy at the primary research

institution. Patients who have given their own consent for this study. Since the amount of surgical smoke emission during laparotomy is considered to be affected by the amount of subcutaneous fat and gender, patients will be randomly assigned to a group with or without surgical smoke evacuation device based on age, gender, and body mass index.

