## 6. Rationale for the scientific rationale of the study

[figure not shown]
Smoke generated during surgery was collected and measured for the purpose of evaluating the operating room environment. After a close examination of the evaluation procedure, we found that there was no process that interfered with normal medical treatment or surgery, and that there was no invasiveness to the patient because we were only collecting smoke generated in the operating room. After explaining the situation to the head of the surgery department, smoke samples were collected and analyzed in the operating room. The operating room environment was evaluated under the following conditions: 3 patients were not using smoke evacuation devices, and 3 patients were using smoke evacuation devices (the smoke evacuation devices were used as samples for clinical evaluation purposes). Toxic substances that were noticeably elevated in the surgical smoke were formaldehyde and acetaldehyde. The results of detected amounts by use vs. non-use of smoke evacuation devices are shown in Figure 4. Comparing the results of the preliminary study with the guideline values of the Ministry of Health, Labor and Welfare's "Study Group on Indoor Air Pollution Problems," it was found that the amount of acetaldehyde detected was higher than the guideline values. Based on these results of the environmental assessment in the operating room, further scrutiny was considered necessary, and this study was planned to take into account various factors such as patients' clinical information (age, gender, body mass index, and with/without smoke evacuation devices).

The results of environmental measurements in the same operating room were used as a reference to calculate the sample size for this study. A sample size test was conducted using SAS, version 9.4 (SAS Institute Inc.) to test the hypothesis that acetaldehyde emissions, which were above the standard value, would decrease from 79.2  $\mu\text{g}/\text{m}^3$  to 24.6  $\mu\text{g}/\text{m}^3$  when smoke evacuation devices were used, with  $\alpha$ : 0.05 and  $\beta$ : 0.1. The required number of subjects was 6 in both groups. The number of persons required for the hypothetical decrease to the guideline value of 48  $\mu\text{g}/\text{m}^3$  was 10 for

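### Patients are allocated on age, gender and BMI, but every endpoint is compared with an unadjusted t-test, which gives up precision if those factors predict smoke output

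*Protocol*

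**What the plan says.** Three parts of the protocol bear on this.

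- **Section 5, selection criteria.** The reason given is that "the amount of surgical smoke emission during laparotomy is considered to be affected by the amount of subcutaneous fat and gender". The consequence is that "patients will be randomly assigned to a group with or without surgical smoke evacuation device based on age, gender, and body mass index". No method (stratification, minimisation), strata or cut-points are named. Age is an allocation factor but is not named as something that affects smoke.
- **Section 6, rationale.** After the pilot measurements, "this study was planned to take into account various factors such as patients' clinical information", with age, gender, body mass index and device use listed.
- **Section 4, analysis method.** One analysis covers the primary endpoint (acetaldehyde) and the secondary endpoints (formaldehyde and particle sizes): "The Student's t-test will be used to compare the detected amounts of acetaldehyde, formaldehyde, and emissions by particle size in the two groups". No adjusted or stratified analysis appears anywhere in the protocol.

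**The concern.** When arms are deliberately balanced on factors that predict the outcome, those factors contribute less to the chance difference between the arms. A two-sample t-test does not know this. It estimates its standard error from the full within-arm spread, including the part the allocation has already balanced. The interval is then wider than the design delivers, and the nominal 5% test rejects less than 5% of the time under the null.

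Even without balancing, adjusting for prognostic baseline factors shrinks the residual variance. Either way, information the study already collects on each patient goes unused in the comparison. What is at stake is precision and some power, not the validity of a positive result.

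**Working it through.** **1. The protocol's own sample-size figures.** Section 6 gives α 0.05, β 0.1, a fall in acetaldehyde from 79.2 to 24.6 µg/m³ (difference 54.6) needing 6 subjects, and a fall from 79.2 to 48 (difference 31.2) needing 10. No SD is given, so these numbers cannot be reproduced directly. Solving the exact two-sided two-sample t power function for the SDs that give each stated number:

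- Read as totals (3 and 5 per arm): SD 8.0–15.2 and 11.3–13.3. A common SD of 11.3–13.3 fits both.
- Read as per arm (6 and 10): SD 23.3–26.2 and 19.2–20.3. No single SD fits both.

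So the largest implied SD is about 26. If α was meant as one-sided, it rises to about 30.

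**2. Power for acetaldehyde.** I assume 20 per arm (40 overall is stated; the ratio is not). The t-test has SE = SD × √(2/20) = 0.316 SD and 38 degrees of freedom. The adjusted model has SE ≈ 0.316 SD × √(1 − R²) and 35 degrees of freedom. For a difference of 31.2:

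| SD | Unadjusted | Adjusted, R² 0.3 |
|---|---|---|
| 13.3 | about 100% | about 100% |
| 20 | 99.8% | above 99.9% |
| 23 | 98.7% | 99.9% |
| 26 | 95.9% | 99.3% |
| 40 | 67% | 82% |

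At SD 26 the gain is 99.3 − 95.9 = 3.4 points (4.1 at R² 0.5). Unadjusted power falls below 90% only if the SD exceeds about 29.7. On the one-sided reading with SD 30, one-sided power is about 94% unadjusted and 99% adjusted at R² 0.3, a gain of 4 points. For a difference of 54.6, unadjusted power is about 100% at every SD up to 26.

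**3. Size of the standard-error problem.** Simulation: 40 patients, 4,000 trials per setting, outcome SD 1, minimisation on gender, BMI and age with probability 0.8 (assumed), R² assumed. Power is at an effect of 1.052 SD, where the t-test has nominal 90% power.

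| R² | Mean t-test SE | True SD of estimate | Ratio | Type I error, t-test | Adjusted SE | Type I error, adjusted | Power, t-test | Power, adjusted |
|---|---|---|---|---|---|---|---|---|
| 0 | 0.314 | 0.316 | 0.99 | 4.9% | 0.319 | 5.1% | 89.7% | 89.0% |
| 0.1 | 0.314 | 0.310 | 1.01 | 4.5% | 0.302 | 5.1% | 90.6% | 91.9% |
| 0.3 | 0.316 | 0.282 | 1.12 | 2.6% | 0.268 | 4.6% | 92.2% | 96.9% |
| 0.5 | 0.317 | 0.259 | 1.22 | 1.7% | 0.227 | 5.2% | 93.9% | 99.4% |

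Across repeat simulations the excess in the SE ranged over about 1–5%, 11–13% and 21–24% for R² 0.1, 0.3 and 0.5. A repeat gave type I error of 3.8%, 2.5% and 1.5%. As a bound, perfect balance would give an excess of 1/√(1 − R²) − 1, that is 5%, 20% and 41%; minimisation achieves part of this. At R² 0.3, adjustment cuts the reported SE by 1 − 0.268/0.316 = 15%.

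**4. If allocation is simple randomisation.** At R² 0.3 the t-test SE (0.315) matches the true SD (0.317) and type I error is 4.9%, so the test is valid. The adjusted SE is 0.274, and power rises from 89.8% to 95.7%.

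**5. Price of adjusting for nothing.** With R² 0 and an effect of 0.9 SD, power falls from 79.3% to 77.6% under minimisation (1.7 points) and from 79.5% to 75.7% under simple randomisation (3.8 points).

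**The case against.** The strongest reply is that nothing here is invalid. The unadjusted difference is unbiased, type I error is at or below the nominal level, and a conservative test cannot produce a false claim that the device works. That stands.

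The size of the effect also rests on two things the protocol does not give: how patients are allocated, and how much of the variation in smoke the factors explain. At R² of 0.1 the loss is negligible. That stands too, and it is why results are shown as a range.

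A reader might infer that the trial is underpowered for acetaldehyde. The protocol's figures do not support this. A power contrast at, say, 0.8 SD would need an SD of 31.2/0.8 = 39 for the smaller planned effect, well above any SD implied by the stated sample sizes.

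A reader might also take section 6 as a promise of covariate adjustment. It lists the factors to be taken into account without saying how, and using them in the allocation could satisfy it.

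Finally, a statistical analysis plan that is not shown may add adjustment. It may, but section 4 does more than stay silent: it names the test for each endpoint, and that test does not use the allocation factors.

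**Conclusion.** The mismatch between allocation and analysis is in the text, and an adjusted analysis would serve the trial better. This is a moderate efficiency point, not a validity error.

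That the t-test runs below 5% is conditional: it requires an allocation that actually balances the arms and factors that predict smoke. It should not be stated as fact. Nor should all three factors be called drivers of smoke; section 5 says this of fat and gender only. Age belongs in the model because it is an allocation factor.

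For the primary endpoint, narrower and correctly sized intervals matter more than power. Power could matter in two places. Formaldehyde and the particle sizes have no sample-size basis in the protocol. And the acetaldehyde SD, which is not stated, rests on a pilot of 3 against 3 patients; if it were 40, power for a fall of 31.2 µg/m³ would be 67% unadjusted against 82% adjusted at R² 0.3. All figures assume 20 per arm and a normally distributed outcome.

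**What to change.** In section 4, make the primary analysis a linear model of acetaldehyde on arm, gender, BMI (continuous) and age (continuous), reporting the adjusted difference with its 95% confidence interval. Use the same model for formaldehyde and each particle size. Keep the unadjusted t-test as a supportive analysis. Fix this before outcomes are seen, so that the choice of covariates cannot look selective.

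The cost is a sentence or two of text and three degrees of freedom (38 to 35), with no new data and no extra patients. If the factors turn out to explain nothing, the loss is about 1–4 points of power at an effect of 0.8–0.9 SD.

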## **5. Selection of research subjects**

[Number of research subjects] Overall expected number of subjects: 40 cases (40 cases at the University of Tokyo)

[Selection criteria]

1. Inclusion criteria

Patients aged 20 years or older undergoing laparotomy at the primary research

institution. Patients who have given their own consent for this study. Since the amount of surgical smoke emission during laparotomy is considered to be affected by the amount of subcutaneous fat and gender, patients will be randomly assigned to a group with or without surgical smoke evacuation device based on age, gender, and body mass index.

## 2. Exclusion Criteria

Patients under 19 years of age. Patients who did not give consent for this study.

## 6. Rationale for the scientific rationale of the study

[figure not shown]
Smoke generated during surgery was collected and measured for the purpose of evaluating the operating room environment. After a close examination of the evaluation procedure, we found that there was no process that interfered with normal medical treatment or surgery, and that there was no invasiveness to the patient because we were only collecting smoke generated in the operating room. After explaining the situation to the head of the surgery department, smoke samples were collected and analyzed in the operating room. The operating room environment was evaluated under the following conditions: 3 patients were not using smoke evacuation devices, and 3 patients were using smoke evacuation devices (the smoke evacuation devices were used as samples for clinical evaluation purposes). Toxic substances that were noticeably elevated in the surgical smoke were formaldehyde and acetaldehyde. The results of detected amounts by use vs. non-use of smoke evacuation devices are shown in Figure 4. Comparing the results of the preliminary study with the guideline values of the Ministry of Health, Labor and Welfare's "Study Group on Indoor Air Pollution Problems," it was found that the amount of acetaldehyde detected was higher than the guideline values. Based on these results of the environmental assessment in the operating room, further scrutiny was considered necessary, and this study was planned to take into account various factors such as patients' clinical information (age, gender, body mass index, and with/without smoke evacuation devices).

The results of environmental measurements in the same operating room were used as a reference to calculate the sample size for this study. A sample size test was conducted using SAS, version 9.4 (SAS Institute Inc.) to test the hypothesis that acetaldehyde emissions, which were above the standard value, would decrease from 79.2  $\mu\text{g}/\text{m}^3$  to 24.6  $\mu\text{g}/\text{m}^3$  when smoke evacuation devices were used, with  $\alpha$ : 0.05 and  $\beta$ : 0.1. The required number of subjects was 6 in both groups. The number of persons required for the hypothetical decrease to the guideline value of 48  $\mu\text{g}/\text{m}^3$  was 10 for

both groups. Considering the possibility of sample collection errors, 40 patients in both groups will be included. Because this study also requires the collection of clinical information on patients, it will be conducted after ethical review.

Figure 4

## 7. procedure for receiving IC

After patients undergoing surgery at the Department are admitted, an explanation and consent for this study will be obtained at the time when other Department-led research is explained during the IC regarding surgery prior to surgery. Patients who have had this study explained to them using the Explanation Document (pp. 13-16) and who have obtained a Consent Form (p. 17) will be considered for this study. A Consent Withdrawal Document (p. 18) will also be distributed to provide an opportunity for withdrawal after consent is given.

## 8. Handling personal information

Surgical-related smoke to be dispersed during surgery will be collected, and clinical information will be collected. Both will be anonymized at the University of Tokyo by creating a correspondence table. The former will be handed directly to the co-researcher at the University of Tokyo in anonymized form on the day the smoke is collected, and the components will be analyzed at the Environmental Technology Center co., Ltd, which is a joint research facility. Clinical information will be collected at the University of Tokyo, and this data will not be passed on to outside parties.

## **9. Burden, risks, and benefits to research subjects**

(1) Physical and psychological burden and potential risks (including cost burden, time, and information leakage)

There is no physical risk because the research will only collect smoke generated during surgery in actual clinical practice. Although the utmost care will be taken in the handling of personal information, there is a possibility of psychological burden in the event of information leakage.

(2) Details of cases in which there is a benefit to the research subject

By analyzing the smoke generated during surgery and elucidating the benefits of using smoke evacuation devices, we may be able to provide insight into the smoke that may be passively taken in by the research subjects themselves. In addition, there is value in contributing to society by elucidating the risks associated with surgical smoke in operating room workers through this research.

(3) Reasons why (1) is inevitable to obtain research results

Because it is essential to handle clinical information of patients (age, gender, body mass index, etc.) in order to compare and study surgery-related smoke.

(4) Measures to minimize the contents of (1)

Maximum care in handling personal information.

## **10. Storage and disposal of samples and information**

This study requires the collection of surgical smears as samples and clinical information as materials.

[Storage and disposal of samples]

Surgical smoke

Storage location: Environmental Technology Center co., Ltd Storage

Method: Refrigerator in the Environmental Technology Center co., Ltd

Time and method of disposal: Date of smoke collection

Clinical information before anonymization

1. Clinical information

Storage location: Medical records of Hepato-Biliary-Pancreatic Surgery Division, Department of Surgery, Graduate School of Medicine, The University of Tokyo

Storage method: In accordance with hospital regulations for medical records

Disposal timing and method: In accordance with hospital regulations for medical records

## 2. Consent and Consent Withdrawal Form

Storage location: Secretarial Office, Hepato-Biliary-Pancreatic Surgery Division, Department of Surgery, Graduate School of Medicine, The University of Tokyo

Storage method: In a locked cabinet

Time and method of disposal: Shredded 10 years after the publication of research results

Information after anonymization and information related to the results of the analysis

Storage location

The University of Tokyo: Secretariat Office, Hepato-Biliary-Pancreatic Surgery Division, Department of Surgery, Graduate School of Medicine, The University of Tokyo (electronically lockable)

Environmental Technology Center co., Ltd: Research room accessible only to research personnel (electronically lockable)

Method of storage

The University of Tokyo: stored in a password-protected computer that cannot be taken out.

Environmental Technology Center co., Ltd: stored on a password-protected computer that cannot be taken out of the building.

Timing and method of disposal

The University of Tokyo: Deleted using data deletion software 10 years after publication of research results.

Environmental Technology Center co., Ltd: 10 years after the publication of the research results, the data will be deleted using data deletion software.

[Correspondence table]

Storage location: Secretarial office of Hepato-Biliary-Pancreatic Surgery Division, Department of Surgery, Graduate School of Medicine, The University of Tokyo (electronically lockable)

Method of storage: In a password-protected computer that cannot be removed from the anonymized database.

Time and method of disposal: Deleted by data deletion software 10 years after the publication of the study results.

